PROTOCOL TITLE

Alleviation of Acute Sore Throat Pain and Inflammation

PRINCIPAL INVESTIGATOR

[name] DO

[name]

[name]

INTRODUCTION/BACKGROUND INFORMATION

The nasopharynx (located between the nose and throat) is the main site of viral replication during upper respiratory infection (URI) (Winther et al 1986). Infections often start in the nose and are carried down to the nasopharynx. The nasopharynx is also the main site of bradykinin release, which would in turn stimulate nociceptive nerves in the throat, hence the feeling of a sore throat following a nasal infection, and a sore throat being among the most common and earliest indicators of an upper respiratory infection such as the common cold or influenza (Eccles 2005).

Despite the plethora of over the counter (OTC) products and supplements available to the US consumer, almost none have shown efficacy for common cold symptoms in clinical studies. A Cochrane meta-analysis found that non-steroidal anti-inflammatory drugs (NSAIDS) such as aspirin when taken orally are “somewhat effective” in relieving discomfort caused by a cold (Kim et al 2015). We have developed three possible treatments with and without aspirin, each containing a mix of several natural compounds which act synergistically to resolve inflammation and prevent damage to the respiratory lining in an effort to treat common cold symptoms.

Bradykinin is a naturally occurring peptide molecule that is one of the first chemical signals generated by pharyngeal cells that will ultimately result in common cold symptoms (Eccles 2005). At least three prior clinical studies have used bradykinin to induce common cold symptoms in healthy subjects (Rees and Eccles, 1994; Doyle, Boehm, and Skoner, 1990; Proud et al., 1988). According to these studies, bradykinin release from the nasopharynx causes inflammation and pain. Each of these studies cites prior *in vitro* research that outlines the biochemical pathways and mechanism of action for this.

Our previous research as well as that of others has shown that bradykinin induces arachidonic acid which then releases COX-1 and COX-2 to increase levels of PGE2, a downstream

inflammatory signal (ref), and that PGE 2 may induce Il-8 as well as other inflammatory chemokines and cytokines.

Acetyl salicylic acid (aspirin) is a COX inhibitor and therefore, a logical option for treating COX-induced inflammation locally. Aspirin is commonly used as a symptomatic treatment for occasional pain, but according to several clinical and laboratory studies, aspirin has strong anti-viral as well as anti-inflammatory properties that can affect cold symptoms and cold duration (Glatthaar-Saalmuler et al 2017; Eccles et al., 2003; Sessa et al., 2017) .

AIMS & OBJECTIVES

We aim to test various treatments against placebo for clinical efficacy against sore throat pain as our primary endpoint and common cold symptoms as our secondary endpoint. Subjects who are affected by mild to severe sore throat pain lasting less than 2 days will be seen virtually by a physician and randomly assigned to receive either placebo or one of three different treatments. Treatment groups will contain placebo and/or a combination of aspirin-based tablets and throat sprays. The study will be conducted in a double-blind format. Only subjects who are unlikely to have a bacterial infection (such as strep throat) based on comorbid symptoms and presence of fever will be enrolled.

The dependent variable will be a visual analog score (VAS) of sore throat pain on a 100mm scale (Sore Throat Pain Intensity Score described below). The visual analog scales used in these studies have been well-validated for sore throat and other types of pain studies (Schactel et al., 2014 and references therein). Secondary endpoints will include changes to the modified Jackson Score.

HYPOTHESES

We hypothesize that subjects receiving spray treatment will report an average sore throat score that is one-half as high as those not receiving treatment and that their sore throat pain will be alleviated significantly faster than subjects receiving placebo. We hypothesize that the aspirin tablet combined with the aspirin and/or wintergreen throat spray will decrease sore throat pain as well as improve Jackson scores for common cold symptoms. This hypothesis is based on our own data using human biopsy tissue showing that Treatment decreases inflammatory prostaglandin production by at least 50% without damaging respiratory tissue and is also based on studies of aspirin treatment for the common cold (Glatthaar-Saalmuller et al., 2017). The Treatment will consist of a formulation of active and inactive ingredients listed in the “Additional Information” section of this protocol. The placebo will consist of vehicle buffer, a sub-therapeutic dose of menthol, and a sweetener. The sub-therapeutic dose of menthol is included so the placebo will taste and smell similar to treatment. Since a multitude of mechanisms contribute to the placebo effect, such as expectations, learning, memory, and motivation (Gupta and Verma 2013), we aim to remove as many stimuli as possible from the placebo group to control for these effects.

METHODS

OVERVIEW OF THE STUDY DESIGN

Subjects will be recruited via targeted social media advertisements (Facebook). Subjects interested in enrolling in the study will call a number listed in the ad or fill out an online form and be called back by the Clinical Trial Manager (CTM).

The CTM will ask potential participants a series of questions on the phone to determine their initial eligibility and enter responses on a digital form (CTM Intake Form) contained on a HIPAA-compliant platform.

The CTM will arrange an in-person visit by the Clinical Trial Administrator (CTA) to the participant's home for that evening as well as a virtual visit by the physician (PI) also for that evening. In addition, the CTM will email participants a copy of the Informed Consent (IC) for them to look over. The CTA will collect a signed physical copy of the IC during their visit as well as baseline sore throat assessments.

The CTA will collect vital signs from each participant during the in-person visit and fill out digital forms (CTA Intake Form). The CTA will also provide the participants with study materials and randomly assigned and double-blinded interventions or placebo.

Subjects will be randomized with respect to which treatment or placebo they receive, and whether they get the placebo or treatment spray or lozenge. The spray will be applied every hour during waking hours and the tablet will be taken every four hours during waking hours. Subjects will be asked not to eat or drink anything for a few minutes after administration.

Subjects will be asked at four-hour intervals during waking hours to rate their sore throat pain on a validated, paper-based sore throat pain scale, Sore Throat Pain Intensity Scale (STPIS) consisting of a 100mm line along which participants mark their pain intensity (Schactel et al., 2014 and references therein).

The study will end when participants complete their second day of treatment and surveys.

The study will be conducted in a double-blind format, neither the participant nor the CTA, CTM, or PI will know whether the participants are getting treatment or placebo. Participants will be coded and randomized by a third party as the treatments are bottled.

The study will only be unblinded at the end of the study after the data analysis has been completed and by the Adverse Events Specialist (AES) in the case of adverse events.

STUDY POPULATION

Healthy adults, half male, half female, aged 18-65 with no history within the past 30 days of serious allergy, asthma, nasal or otologic disease, and no symptoms of upper respiratory infection (URI). After age 65 many of the exclusion criteria listed below become more common. We feel it is important to enroll an equal number of males and females to control for gender bias in the data.

This will be controlled for in the recruitment process and adjusted if needed by controlling social media targeting criteria. Initially the target population will be: age 18-65, living in the Washington DC/northern Virginia area, retired, government employee, teacher, non-active duty military personnel, or college student.

INCLUSION AND EXCLUSION CRITERIA

Inclusion

Healthy adults between the ages of 18-65 that do not meet any of the exclusion criteria listed below, and who rate their sore throat at least a 3 on a 10 point scale, and who have had a sore throat for less than 48 hours by the time they complete the CTM assessment.

Exclusion

Sore throat for more than 2 full days at the time of CTM assessment

Fever or development of fever during the course of the trial

Positive COVID-19 test or influenza test at CTA visit

Likelihood of strep throat (to be determined by PI to the best of their ability)

Less than 2 doses of the COVID vaccine

Any allergies to eggs, milk, or aspirin

Females who are pregnant or test positive for pregnancy at the CTA visit

Any chronic disease such as asthma, hypertension, post-nasal drip, gastroesophageal reflux disease (GERD), cardiopulmonary obstructive disorder (COPD), diabetes, cancer, HIV

Any history of allergy in the last 14 days for which they took medication

Anyone with fever above 101 or who has taken medication other than birth control in the last 30 days

Anyone taking an ACE inhibitor

Participation in another clinical trial within the last 6 months or during this trial

Anyone who smokes

STATISTICAL CONSIDERATIONS

ANALYSIS PLAN

The design of this study will be a between patient, non-crossover, randomized controlled trial. The primary endpoint of this study is a time-weighted summed difference in pain intensity on the sore throat pain intensity scale over 36 hours after the first dose of medication (STPIS 1st entry Day 1 compared to STPIS 4th entry Day 2). For the study to have 80% power and 20% effect size, we believe we will need at least 100 participants per condition. Our hypothesis is that the patented Mucosal Immune Complex (MIC) will decrease STPIS score by 25-50%. Our assumptions and our hypothesis are based on a previous study utilizing this endpoint with an average baseline STPIS score of 79.1 (+/- 8.2) (Schachtel et al., 2014). Assuming a 50% drop-out or exclusion rate, we aim to enroll a total of 400 participants across all four conditions.

Efficacy will be determined by t-test comparing time-weighted summed differences in STPIS scores for placebo and MIC treatment groups. Secondary endpoints will include changes in STPIS at different time points and changes in Modified Jackson Score over the course of the study.

SAMPLE SIZE JUSTIFICATION

Based on a similar prior study of an NSAID containing lozenge for sore throat (Schachtel et al., 2014) a 59% decrease in time weighted summed difference for STPIS over 24 hours was seen with a p-value less than 0.01 with a sample size of 198 participants.

PROCEDURES AND DATA COLLECTION

Paper-based Patient Forms will be mailed to a PO Box monitored by the PI and the DA, located in Rockville MD. Survey assessments will be measured in mm from the beginning of the line and recorded on an Excel spreadsheet according to kit number (Participants will not be identified by name).

FOLLOW-UP

Participants will be able to contact the PI, CTA, and CTM at any point during the trial. They will be encouraged to contact the trial staff should they suspect any adverse events including fever above 101 at which point a determination will be made by the PI or AES if they should continue. Participants will not be followed after the study ends. Other serious adverse events that the PI will discuss with participants include nausea or vomiting, difficulty breathing, and/or breaking out in a rash or hives.

If anyone else should require information gathered from this study, they will only receive the participant's code number, age, sex, ethnicity, but no other identifying information.

DATA AND SAFETY MONITORING

Participants will self monitor at home and fill out the survey questionnaire at the required time points. Participants will be encouraged to call 911 in case of emergencies such as anaphalactic shock and high fever. The PI and CTM will be available for questions and non-urgent matters.

The AES will be available to address serious adverse events and will unblind the study in cases such as high fever where the participant may be harmed by being in the placebo group, or for any other medically necessary reason.

DISCONTINUATION OF RESEARCH PARTICIPANTS/WITHDRAWAL

Participants will be able to voluntarily discontinue at any point in the study by calling the CTM.

RECORD RETENTION

In the event of any publication or presentation resulting from the research, no personally identifiable information will be shared.

REPORTABLE EVENTS

As required by Policy IRB-01, all reportable events will be reported to the IRB within the specified deadlines. Additional information is provided in the IRB Guidance on “Reportable Events.” Events are defined in the IRB Guidance on “Acronyms and Definitions.” For additional information see: <http://research.downstate.edu/irb/irb-policies.html>

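### The protocol both matches the placebo to treatment and aims to strip stimuli from the placebo group alone; only matching controls placebo effects, and stripping would bias a self-rated pain comparison toward treatment

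*Combined protocol and SAP*

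**What the plan says.** In Hypotheses, the protocol gives the composition of the placebo: "The placebo will consist of vehicle buffer, a sub-therapeutic dose of menthol, and a sweetener". It does not say whether this describes the spray, the tablet or both. It then gives the reason for the menthol: "The sub-therapeutic dose of menthol is included so the placebo will taste and smell similar to treatment". The next sentence lists expectations, learning, memory and motivation as sources of the placebo effect and ends: "we aim to remove as many stimuli as possible from the placebo group to control for these effects".

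The same section describes the products under test as "the aspirin tablet combined with the aspirin and/or wintergreen throat spray". For the treatment ingredients it refers to an Additional Information section, which is not in the text available for this review.

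Under Overview of the Study Design, the trial is double-blind: "neither the participant nor the CTA, CTM, or PI will know whether the participants are getting treatment or placebo". A third party does the coding when the products are bottled. The spray is used hourly and pain is rated every four hours while awake, on a scale "consisting of a 100mm line along which participants mark their pain intensity". The Analysis Plan states: "Efficacy will be determined by t-test comparing time-weighted summed differences in STPIS scores for placebo and MIC treatment groups".

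The available text describes no check of sensory similarity between products and no assessment of blinding.

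**The concern.** The two neighbouring sentences give opposite instructions for the control product. The first makes the placebo more like treatment. The second makes the placebo group's experience poorer, and it names that group only. Whoever prepares the placebo cannot follow both.

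The stated reason for the second aim is also mistaken. A placebo arm controls for expectation and learning by reproducing them, so that they drop out of the between-arm difference. Taking the triggers away from the control arm does not take them away from the active arms.

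Two things would be at stake if the aim were followed. Participants could recognise their arm, which would undermine the blinding. And any response to taste, smell or expectation that occurs only in the active arms would be counted as efficacy. The participant is also the outcome assessor, and no objective endpoint is listed to set against the rating.

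**Working it through.** The protocol gives no figure on this point, so there is none to reproduce. The check is a comparison of texts, then a statement of the bias, then an illustration on assumed values.

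**1. The texts side by side.**

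| Statement | Location | Effect on arms |
|---|---|---|
| Menthol added for similar taste and smell | Hypotheses | Brings placebo closer to treatment |
| Aim to remove stimuli from the placebo group | Hypotheses, a following sentence | Moves placebo away from treatment |
| Placebo is vehicle buffer, menthol and sweetener | Hypotheses | No named counterpart to wintergreen |
| Double-blind, coded by a third party | Overview of the Study Design | Requires arms to be indistinguishable |

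The stripping aim conflicts with both the menthol sentence and the double-blind format.

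**2. Direction of the bias.** Let τ be the effect of the active ingredients. Let e(T) and e(P) be the relief produced by stimuli and expectation in the treatment and placebo arms. If these add, then

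expected difference = τ + [e(T) − e(P)].

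With matched arms, e(T) = e(P) and the difference is τ. Removing stimuli from placebo lowers e(P) only, so the bracket becomes positive and adds its full size to the estimate, in favour of treatment.

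**3. Exposure.** With hourly sprays and four-hourly ratings, there are about 4 ÷ 1 = 4 sprays between consecutive ratings. Any perceptible difference would be met repeatedly.

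**4. Illustration only.** Let b be the bracket in step 2, in SD units of the primary endpoint. No value of b appears in the documents. Assume that the drug has no effect, a two-sided alpha of 0.05 (the plan states none) and a normal approximation:

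P(significant in favour of treatment) = Φ(b / √(2/n) − 1.96).

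The Analysis Plan gives 100 per condition, a total of 400 over four conditions, and 50% loss. With equal allocation (assumed), 400 ÷ 4 = 100 enrolled per arm, and 100 × 0.5 = 50 remain after that loss.

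| Assumed b | n = 100 per arm | n = 50 per arm |
|---|---|---|
| 0 (matched) | 2.5% | 2.5% |
| 0.1 SD | 10.5% | 7.2% |
| 0.2 SD | 29.3% | 16.9% |
| 0.4 SD | 80.7% | 51.6% |

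Example for b = 0.2, n = 100: √(2/100) = 0.1414; 0.2/0.1414 = 1.414; 1.414 − 1.96 = −0.546; Φ(−0.546) = 29.3%.

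A larger sample makes the false positive more likely, so sample size is no protection. Converting b to millimetres would need the SD of the time-weighted summed difference. The plan gives only a baseline spread of 8.2, from another study.

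**The case against.** The strongest case on the other side is that this is loose wording in a rationale. Nothing in Methods carries out the stripping aim. The only concrete formulation measure, the menthol, works toward matching, and the double-blind format with third-party coding points the same way. The word used is stimuli, in a sentence about expectation, learning, memory and motivation, so reading it as sensory is an interpretation. The sentence could be a clumsy way of saying that cues which identify the placebo should be kept to a minimum.

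Wintergreen needs care as well. The treatment ingredient list is in a section not available here, and the contents of the vehicle buffer are not given. Wintergreen is named as a treatment spray, so adding it to the placebo could put a hypothesised active component in the control. Relief from such a component may be treatment effect, not bias. Aims & Objectives also indicates that a treatment group may receive placebo for part of its regimen, so a uniform cue across the three active arms is not established.

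All of this stands, and it limits the point. A reader might infer that the trial's treatment difference is in fact inflated, or that its blinding fails. The documents do not support either inference: they do not show that any stimulus was removed or that the finished products can be told apart. But none of these arguments reconciles the two sentences or makes an aim directed at the placebo group alone a sound control for placebo effects. That remains true for any kind of stimulus, sensory or not.

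**Conclusion.** The contradiction is established from the text, and the stripping aim is wrong in principle. The bias is conditional. If stimuli were removed from the placebo only, blinding could be lost and the difference on the self-marked pain line would be biased toward treatment.

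The documents do not allow the size to be estimated. The false-positive percentages rest on an assumed imbalance, no drug effect, a two-sided alpha of 0.05, equal allocation and a normal approximation. They show only that a modest imbalance could matter; they do not show that one exists.

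The absence of a named match for the wintergreen spray is a question to settle against the full ingredient list, not a demonstrated mismatch. The correction should be made: the direction of the possible bias is clear and the cost is low.

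**What to change.** 1. Delete the aim of removing stimuli from the placebo group. Replace it with: *The placebo spray and tablet are matched to the treatments for taste, smell, appearance and mouth-feel, as far as this is possible without adding a hypothesised active component.*
2. Reconcile the listed placebo contents with that statement, separately for spray and tablet, and say how each treatment spray, including wintergreen, is matched or why it cannot be. Wintergreen in the placebo is not required.
3. Where matching is not achieved, limit the conclusion to the effect of the product including its sensory effect, and do not attribute the difference to the active ingredients alone.
4. Optionally, add one question to an existing paper form asking which treatment the participant thinks they had and why (taste, relief, other). Report the answers descriptively by arm, noting that a correct guess can also reflect real relief.

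The cost is a change of protocol wording, possibly a minor flavour adjustment of the placebo, and one extra form item if the option is taken. The observed difference from placebo may be smaller.

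### The 50:50 sex quota fixes the overall mix but not the balance between the four conditions; adding sex to the primary model would recover a small loss of precision

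*Combined protocol and SAP*

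**What the plan says.** The Study Population section describes the sample as "Healthy adults, half male, half female, aged 18-65", and gives the reason: "We feel it is important to enroll an equal number of males and females to control for gender bias in the data". The means follows directly: "This will be controlled for in the recruitment process and adjusted if needed by controlling social media targeting criteria".

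Allocation is described elsewhere. Aims & Objectives has subjects "randomly assigned to receive either placebo or one of three different treatments". The Overview of the Study Design adds: "Participants will be coded and randomized by a third party as the treatments are bottled". Neither section mentions stratification, blocking or minimisation by sex.

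The Analysis Plan bases efficacy on a t-test of the time-weighted summed differences, placebo against treatment, with no covariates. It sets the trial's size: "we aim to enroll a total of 400 participants across all four conditions". The Follow-up section lists sex among the items held with a participant's code number.

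**The concern.** A quota on the total and balance between conditions are different things. A trial with exactly 200 men and 200 women can still have, by chance, 56 men among 100 on placebo and 45 among 100 on an active treatment. The treatment comparison depends on that second kind of balance, and advertisement targeting cannot influence it.

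The sponsor has named sex as a variable to control, yet sex enters neither the allocation as described nor the analysis. If self-rated throat pain or its course differs between the sexes, part of the outcome variance could be removed from each comparison, and the planned test leaves it in. A visible sex gap between conditions could also prompt an unplanned adjusted analysis after unblinding, which is harder to defend than one specified beforehand.

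**Working it through.** The plan gives no figure for sex balance, so there is none to reproduce. Its sample-size figures are used only as arm sizes.

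**Inputs from the documents**
- Four conditions; 400 enrolled; half male, half female.
- Loss: "Assuming a 50% drop-out or exclusion rate", which leaves about 50 of 100 per condition.
- Primary analysis: unadjusted t-test.

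**Assumptions**
- Equal allocation, taken from 400 across four conditions; the ratio is not stated.
- Allocation not restricted by sex, since no restriction is described.
- Each active condition compared with placebo.
- Losses at random.
- Two-sided 5% level for the type I error check; the plan states no level.
- A sex effect g of 0.2 to 0.5, in units of the within-sex SD.

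**Step 1. Does the quota narrow the gap between conditions?**

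With an exact quota, the number of men m in a condition of n = 100 out of N = 400 (200 male) is hypergeometric:
- Var(m) = n × 0.25 × (N − n)/(N − 1) = 100 × 0.25 × 300/399 = 18.80
- Cov between two conditions = −n² × 0.25/(N − 1) = −100 × 100 × 0.25/399 = −6.27
- Var(difference) = 2 × 18.80 + 2 × 6.27 = 50.1, so SD = 7.08 men per 100, or 7.08 percentage points

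With no quota and the same expected mix, Var(difference) = 2 × 100 × 0.25 = 50, so SD = 7.07 points. With no quota and an assumed 70:30 mix, SD = √(2 × 0.7 × 0.3/100) = 6.5 points. The quota does not narrow the gap.

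**Step 2. How large are the gaps?** (200,000 random draws, quota met exactly)

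| Per condition | SD of gap | Gap of 10 points or more, one comparison | In at least one of three comparisons with placebo |
|---|---|---|---|
| 100 | 7.1 points | 18% | 40% |
| 50 | 10.0 points | 37% | 70% |

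**Step 3. What does a gap do to the treatment estimate?**

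A gap of 10 points shifts a contrast by 0.10 × g:
- g = 0.2: 0.02 SD
- g = 0.5: 0.05 SD

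The standard error of the contrast is √(2/n) = 0.14 SD at 100 per condition and 0.20 SD at 50. The shift is therefore at most about a third of one standard error (0.05/0.14 = 0.36).

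**Step 4. Is the t-test still valid?**

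In 20,000 simulated null trials with 100 per condition, g = 0.5 and allocation ignoring sex, the unadjusted t-test rejected in 4.9%. There is no inflation.

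**Step 5. What precision is lost?**

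In a 50:50 sample, sex adds 0.25g² to a within-sex variance of 1, so the standard error is multiplied by √(1 + 0.25g²):
- g = 0.2: √1.01 = 1.005, an increase of 0.5%
- g = 0.5: √1.0625 = 1.031, an increase of about 3%

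The share of total variance that adjustment could recover is 0.01/1.01 = 1% to 0.0625/1.0625 = 6%. The ratio is the same at either arm size.

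**Step 6. Would stratifying the kits by sex be enough?**

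Suppose every condition starts with exactly 50 men and 50 women and half are then lost at random:
- Var(m) = 50 × 0.25 × 50/99 = 6.31
- SD of the gap = √(2 × 6.31)/50 = 7.1 points

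The chance that at least one active condition then differs from placebo by 10 points or more is 44% (400,000 draws). Stratified kits would reduce the SD from 10.0 to 7.1 points but would not remove the gap.

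**The case against.** The strongest reply is that the plan never claims the quota balances the conditions. It does not define gender bias, and the phrase may mean over-representation of one sex in the sample, which a quota does address. This stands. A reader might infer that the plan's stated control is missing, or that the plan depends on it, but the documents support neither reading. The control it states, equal enrolment through recruitment, is described, and nothing in the sample size or analysis text rests on it.

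A reader might also infer that the placebo comparisons are biased by sex. They are not. Randomisation balances sex in expectation, and the t-test's standard error already allows for chance imbalance, as Step 4 shows. The 40% and 70% figures are chances of crossing an arbitrary threshold in sex mix, not effects on the pain score.

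Nor do the documents show that stratification is absent. They say that a third party randomises at bottling and give no further detail, so it is unspecified. They also do not say whether anyone's sex is known at that point.

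What the reply leaves standing is that the plan names sex as a variable to control, specifies nothing that acts between conditions, and already holds the data needed to do so.

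**Conclusion.** The point holds as a minor one. The quota sets the overall sex mix and has no effect on balance between conditions (7.08 against 7.07 points), and no control by sex between conditions is specified in allocation or analysis. The consequence is a standard error about 0.5% to 3% larger than necessary. That range depends on the assumed sex effect of 0.2 to 0.5 SD; if sex has no effect on the endpoint, nothing is lost. The imbalance figures also assume equal allocation that is not restricted by sex, and losses at random. Neither the validity of the primary comparison nor its type I error is in question.

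**What to change.** 1. In the Analysis Plan, replace the t-test with a linear model of the time-weighted summed difference in pain score on treatment condition, with sex as a pre-specified factor. Report each contrast with placebo from that model. The text should be fixed before unblinding.
2. In Study Population, reword the quota sentence to say that equal enrolment serves representation of both sexes, and refer to the model for control between conditions.
3. Stratifying the kits by sex is optional and secondary, given Step 6. If the third party already does so, the protocol should say so.

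The cost is two sentences of text and linking sex, already held with the code number, to the pain scores recorded by kit number. No extra participants or assessments are needed. Other covariates are a separate matter. For example, the 48-hour entry limit does not show that hours since onset are recorded, so adding that variable cannot be assumed to be free.

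### The substance-based allergy exclusion stops at egg, milk and aspirin and leaves out wintergreen, menthol and the sweetener, which the protocol names in study products (minor)

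*Combined protocol and SAP*

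**What the plan says.** Under Inclusion and Exclusion Criteria, the one bullet that names allergens reads "Any allergies to eggs, milk, or aspirin". It ends there, with no general clause for other components of the products.

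The Hypotheses section names further components. It refers to the "aspirin tablet combined with the aspirin and/or wintergreen throat spray", and states: "The placebo will consist of vehicle buffer, a sub-therapeutic dose of menthol, and a sweetener". It explains the menthol as follows: "The sub-therapeutic dose of menthol is included so the placebo will taste and smell similar to treatment". The Introduction adds that there are three treatments, "each containing a mix of several natural compounds", which it does not name. For the full composition the Hypotheses section points elsewhere: "The Treatment will consist of a formulation of active and inactive ingredients listed in the" Additional Information section. That section is not in the text available for this review.

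Three other rules bear on allergy, and each looks back over a limited period:

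- Study Population requires no serious allergy in the preceding 30 days.
- An exclusion bullet removes anyone with an allergy in the preceding 14 days that they treated with medication.
- Another bullet removes anyone who used any medication, birth control apart, in the preceding 30 days.

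The spray is used hourly while awake until the end of the second day (Overview of the Study Design). Participants monitor themselves at home, and Data and Safety Monitoring says: "Participants will be encouraged to call 911 in case of emergencies such as anaphalactic shock and high fever".

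**The concern.** Excluding people allergic to aspirin shows that the protocol already treats allergy to a study ingredient as a reason not to enrol. The list does not carry that principle through to the other ingredients the protocol names. A person who knows they react to menthol, wintergreen or the sweetener could meet every written criterion and be handed a product containing it.

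What is at stake is the safety of a small number of participants. Dosing is repeated and takes place at home, no staff are present after the first visit, and the written response to a severe reaction is an emergency call. For an allergy the person already knows about, asking beforehand is the simplest protection.

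**Working it through.** There is no figure in the plan to reproduce, and no formula applies. The check sets each named ingredient against each allergy-related criterion.

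**Step 1: ingredients against the named list.**

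| Component | Where the protocol places it | On the named list? |
|---|---|---|
| Aspirin | Tablet; spray, as one of two and/or options | Yes |
| Wintergreen | Spray, as the other and/or option | No |
| Menthol | Placebo, stated; active products, not stated | No |
| Sweetener (type not given) | Placebo, stated | No |
| Several natural compounds | All three treatments; not named in the available text | Cannot be checked |

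Three named components (wintergreen, menthol, sweetener) are not covered by name.

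**Step 2: what the time-limited rules add.**

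- The serious-allergy rule catches a serious episode in the last 30 days.
- The treated-allergy rule catches an episode in the last 14 days for which medication was taken.
- The medication rule catches any drug use in the last 30 days other than birth control. It therefore takes in most of what the treated-allergy rule catches, over a longer window.

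Together the three look back no further than 30 days, and each needs a recent event: a serious episode or the use of a medicine.

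**Step 3: test case.** Take an otherwise healthy adult who knows that menthol gives them hives, avoids it, and has had no reaction and taken no medicine in the last 30 days.

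- Named list: not met, because menthol is not on it.
- Serious allergy within 30 days: not met.
- Treated allergy within 14 days: not met.
- Medication within 30 days: not met.
- The bullet on chronic disease has open wording, but its examples are conditions such as asthma and diabetes. Allergy has its own bullets, so the chronic-disease bullet is not a natural place to look for it.

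No written exclusion applies. The same holds with wintergreen or the sweetener in place of menthol.

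**Step 4: does exposure follow?** Someone in the trial receives the placebo product, and at least one spray is described as possibly containing wintergreen. Aims and Objectives allows treatment groups to include placebo components, so the placebo product may reach more than one arm; the text does not say how many. Whichever it is, the trial gives at least menthol and the sweetener, which the exclusion does not cover.

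**The case against.** The strongest reply is that the written bullets are not the whole of screening. The CTM asks a series of questions by telephone, the CTA visits, the PI sees each participant by video, and the consent form is sent ahead. Any of these could raise ingredients or other allergies, and the full ingredient list sits in a section that cannot be seen here. This stands as a limit: the finding concerns the criteria as written, and what staff would do in practice is unknown. It does not remove the gap, because nothing in the available text says that any of these contacts covers the other ingredients. The absence of the Additional Information section from this copy is not counted against the plan.

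Several stronger readings are tempting and are not supported:

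- *Every spray contains wintergreen or menthol.* Wintergreen appears only as an and/or option. Menthol and the sweetener are stated only for the placebo; that the menthol is there to match taste and smell suggests a similar flavour in the active products, but does not say so.
- *The rash, hives, breathing difficulty and anaphylaxis that the protocol mentions are expected from these ingredients.* The Follow-up and Data and Safety Monitoring sections attribute them to no ingredient, and the trial also gives aspirin. The same sections say that the PI will discuss such events with participants and that staff can be reached throughout.
- *Reactions would cause enough dropout, unblinding or imbalance between arms to disturb the result.* With few people affected, this is speculation.

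**Conclusion.** The point holds as a minor one. The named allergy exclusion is narrower than the set of ingredients that the protocol itself describes, and the time-limited rules leave one clear case uncovered: a known allergy whose trigger has been avoided.

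The number affected is likely to be small. The documents give no prevalence for these allergies, and the number of arms exposed to each ingredient is unclear, so no count can be derived. There is no material effect on power, alpha or the primary analysis. The case for change rests on participant safety and its low cost.

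The conclusion assumes that the bullets are applied as written and that no unseen form or section already contains a general ingredient-allergy rule. If one does, all that remains is to bring the bullet into line with it.

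**What to change.** Reconcile the allergy bullet with the full ingredient list in the Additional Information section. Extend it to known allergy or hypersensitivity to any ingredient of any study spray or tablet, active or placebo. General wording is safer than adding only the three ingredients identified here, because the text available for this review does not name the remaining compounds.

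Ask the matching question on the CTM Intake Form, with the full list in front of the caller. Apply it alike to all arms, so that it gives no hint of allocation.

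The cost is one revised eligibility line, one telephone question and a few extra screen failures. No dose, schedule, endpoint or analysis changes.
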